#### End of Study

The end of the treatment period is defined as the date when the last patient, last visit (LPLV) at 96 weeks occurs (or at Week 100 in the substudy).

#### Length of Study

The total length of the study is expected to be approximately 4 years from the first patient enrolled to LPLV.

The end of study is defined as the LPLV of the safety follow-up.

#### Investigational Medicinal Products

#### Test Product (Investigational Drug)

Dose 1 of ocrelizumab will be administered as two 300-mg IV infusions (600 mg total) separated by 14 days (i.e., Days 1 and 15). Subsequent doses will be administered as one 600-mg IV infusion every 24 weeks, for a maximum of 4 doses.

#### Non-Investigational Medicinal Products

Premedicate with 100-mg methylprednisolone (or equivalent) completed approximately 30 minutes prior to each ocrelizumab infusion and with an antihistaminic drug (e.g., diphenhydramine) approximately 30 – 60 minutes before each infusion of ocrelizumab to reduce the frequency and severity of infusion-related reactions (IRRs).

The addition of an antipyretic (e.g., acetaminophen/paracetamol) may also be considered to further reduce the frequency and severity of IRRs.

#### Statistical Methods

#### Primary Efficacy Outcome Measures

The primary efficacy assessment will be the proportion of patients who are free of any protocol-defined events during a 96-week period. The definition of a protocol-defined event is the occurrence of at least one of the following while on treatment with ocrelizumab:

- A protocol-defined relapse
- A T1 Gd-enhanced lesion on brain MRI
- A new and/or enlarging T2 lesion on brain MRI
- Confirmed disability progression (24 weeks)

#### Determination of Sample Size

Assuming a) the expected proportion of patients who will be event free during 96 weeks is 45%; b) the type one error rate is 5% and the half-width of 95% confidence interval (CI) for the proportion is 4%; c) the probability that half-width of 95% CI is at most 4% is 80%, then the required sample size will be  $n = 600$ .

#### Interim Analyses

It is estimated that two to three interim analyses will be performed during the course of the study, according to patient enrollment and availability of data of interest. Interim analyses may be used for internal decision making, hypothesis generation, abstraction/publication for major MS conferences, or other purposes, as applicable. Details on the timing and scope of interim analyses will be described in the Statistical Analysis Plan

## Appendix 2.

### 2.2 OUTCOME MEASURES

#### 2.2.1 Primary Efficacy Outcome Measures

The primary efficacy assessment is defined as the proportion of patients who are free of any protocol-defined events during a 96-week period. The definition of a protocol-defined event is the occurrence of at least one of the following while on treatment with ocrelizumab:

1. A protocol-defined relapse (an adjudication of protocol-defined relapses will be performed by the sponsor based on pre-specified criteria, applied to data collected by the investigator)
2. A T1 Gd-enhanced lesion on brain MRI
3. A new and/or enlarging T2 lesion on brain MRI
4. Confirmed disability progression (24 weeks)

The evaluation of T1 Gd-enhanced lesions and new and/or enlarging T2 lesions will be performed by NeuroRx and detailed in protocol MN30035 imaging review charter.

#### 2.2.2 Secondary Efficacy Outcome Measures

- The proportion of patients free from a protocol-defined event during a 24-week period and a 48-week period
- Time to protocol-defined event (as defined in [Section 2.2.1](#) above)
- The time to onset of first relapse
- Time to onset of first T1 Gd-enhanced lesion
- Time to onset of first new and/or enlarging T2 lesion
- Time to onset of confirmed disability progression for at least 24 weeks during the study period
- Annualized relapse rate at week 96
- Total number of T1 Gd-enhanced lesions detected by brain MRI at weeks 24, 48, and 96
- Total number of new and/or enlarging T2 lesions detected by brain MRI at weeks 24, 48, and 96

- Change in total T2 lesion volume detected by brain MRI from baseline to weeks 24, 48, and 96

### **2.2.3 Exploratory Efficacy Outcome Measures**

- Change in neurological exam score (EDSS) at Weeks 24, 48 and 96 from baseline
- Percent change in brain volume at Weeks 24, 48, and 96 from baseline
- Change in Patients Reported Outcome Scales from baseline:
  - MSIS-29 - The Multiple Sclerosis Impact Scale
  - SATMED-q - The Treatment Satisfaction with Medicines Questionnaire
  - TSQM II - The Treatment Satisfaction Questionnaire for Medication Version II

### **2.2.4 Pharmacokinetic Efficacy Outcome Measures**

Not Applicable to this study.

### **2.2.5 Safety Outcome Measures**

- Frequency of patients with the following events:
  - Treatment emergent adverse events
  - Serious treatment emergent adverse events
  - Adverse events leading to treatment discontinuation (dose withdrawal)
  - Serious adverse events leading to treatment discontinuation (dose withdrawal)
  - Adverse events leading to infusion dose modification/interruption
  - Serious adverse events leading to infusion dose modification/interruption
  - Treatment-related adverse events
  - Treatment-related serious adverse events
  - Adverse events with fatal outcome
  - MS Relapses

- MS relapses classified as serious
- Infusion-related reactions (IRR):
  - IRR by infusion (dose 1 day 1, dose 1 day 15, dose 2, dose 3, dose 4, overall)
  - IRR by CTCAE grades
  - Infusion related reactions by infusion, grade, and by pre-medication (Methylprednisolone only, Methylprednisolone and analgesics/antipyretics, Methylprednisolone and antihistaminics, Methylprednisolone and analgesics/antipyretics and antihistaminics)
- Time to withdrawal from the study due to an adverse event
- Changes from baseline and select laboratory abnormalities for the following assessments:
  - Hematology (hemoglobin, hematocrit, platelet count, RBC count, WBC count, percent, and absolute differential count [neutrophils, bands, eosinophils, lymphocytes, monocytes, basophils, other cells])
  - Serum Chemistries (AST, ALT, gamma-glutamyl transpeptidase [GGT], total bilirubin, urea, uric acid, creatinine, potassium, sodium, calcium, phosphorus) Urinalysis (specific gravity, pH, glucose, protein, ketones, and blood)
  - B-cell depletion and recovery (CD19+) and T-cell counts (CD4+, CD8+)
  - HBV DNA
  - Vital signs (infusion and non-infusion visit)
- Exposure duration and dose
- Summary of previous DMTs and last DMT before switching to ocrelizumab

## 2.3 DETERMINATION OF SAMPLE SIZE

Assuming a) the expected proportion of patients who will be event free during 96 weeks is 45%; b) the type one error rate is 5% and the half-width of 95% confidence interval for the proportion is 4%; c) the probability that half-width of 95% confidence interval is at most 4% is 80%, the required sample size for this study is n=600. The shorter infusion

substudy will enroll approximately 100 patients. Please refer to protocol for further details.

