4.6.3 Study Treatment Discontinuation

Patients must discontinue study treatment if they experience any of the following:

- Life-threatening IRR or serious hypersensitivity reaction

Ocrelizumab—Genentech, Inc.
40/ Protocol MN30035, Version 5

- Active hepatitis B infection
- PML
- Active TB, either new onset or reactivation

The primary reason for study treatment discontinuation should be documented on the appropriate eCRF. Patients who discontinue study treatment prematurely will not be replaced.

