6.1 DETERMINATION OF SAMPLE SIZE

[figure not shown]
Assuming a) the expected proportion of patients who will be event free during 96 weeks is 45%; b) the type one error rate is 5% and the half-width of 95% CI for the proportion is 4%; c) the probability that half-width of 95% CI is at most 4% is 80%, then the required sample size will be $n=600$.

It should be noted that the estimation of the proportion of patients who will be protocol-defined event free (45%) is based on the pooled data from Studies WA21092 and WA21093 (OPERA I and OPERA II, respectively) from all patients who had a baseline EDSS of ≥ 2.0 . The true proportion could be lower than 45% for ocrelizumab-treated patients who would meet the definition of sub-optimal responders as specified in this protocol. However, the required sample size should be lower than 600 patients to achieve the same precision (i.e., maximum half-width of 95% CI) if the true proportion is actually lower than 45%. This is due to the fact that a lower proportion will have a smaller variance for the estimated proportion than that from 45% and the variance of proportion is maximized when the proportion is 50% (calculation performed using SAS software, Version 9.2). In [Figure 3](#), the sample sizes are displayed from a range of proportions (30% to 50%) with an 80% probability that half-width of 95% CI is at most 4%. For example, if the proportion is 45%, the corresponding sample size is 598.86 (rounded to 600 for recommended number). The ranges of proportion were based on the 2-year proportion of alemtuzumab-treated patients and natalizumab-treated patients who achieved no evidence of disease activity (NEDA) (32% and 55%, respectively). In [Figure 4](#), the sample sizes are displayed similarly to [Figure 3](#), but the

Ocrelizumab—Genentech, Inc.
60/ Protocol MN30035, Version 5

[figure not shown]
half-width of 95% CI is set as 5% for providing additional information concerning the impact of half-width on sample size.

Figure 3 Prob(Half-width of 95% CI \leq 4%) with Sample Size if Expected Proportion=30%–50%

Source: Hartung et al. 2013; Prosperini et al. 2012; Internal OPERA study data.
CI=confidence interval.

Figure 4 Prob(Half-width of 95% CI \leq 5%) with Sample Size if Expected Proportion=30%–50%

Source: Hartung et al. 2013; Prosperini et al. 2012; Internal OPERA study data.
CI=confidence interval.

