Appendix 2 **Optional Shorter Infusion Substudy (cont.)**

Handling of Missing Data

For adverse events with a missing onset date, data will be imputed.

Missing assessments for continuous variables, such as physical examinations and vital signs, will not be imputed.

Determination of Sample Size

Based on the sample size of 100 patients used for analysis, the 95% CIs for some assumed Grade 3 or 4 IRRs are provided in Table 2.

Table 2: Determination of Substudy Sample Size

Number of Patients with Grade 3 or 4 IRRs	Grade 3 or 4 IRRs (%) (N=100)	95% CIs for Grade 3 or 4 IRRs (%)
1	1.00	(0.03, 5.45)
2	2.00	(0.24, 7.04)
3	3.00	(0.62, 8.52)
4	4.00	(1.10, 9.93)
5	5.00	(1.64, 11.28)
6	6.00	(2.23, 12.60)
7	7.00	(2.86, 13.89)

The 95% CIs for the IRR (%) are calculated based on the Clopper and Pearson method.

Appendix 2

Optional Shorter Infusion Substudy (cont.)

Table 3: Substudy Schedule of Activities

	Week 96 Treatment Visit (± 14 days)	Substudy Follow-up Visit (30 ± 14 days later) ^a
Informed consent^b	x	
Review inclusion and exclusion criteria	x	
Physical examination^c	x	x
Weight	x	
Vital signs^d	x	x
Brain MRI^e	x	
Pregnancy test^f	x	
Adverse event assessment^g	x	x
Concomitant treatment review	x	x^h
Methylprednisolone and antihistamine premedicationⁱ	x	
Ocrelizumab administration	x	

eCRF=electronic case report form; IRR=infusion-related reaction; IV=intravenous; MRI=magnetic resonance imaging; PML=progressive multifocal leukoencephalopathy.

^a Conducted 30 days after the shorter infusion with ocrelizumab.

^b Written informed consent will be obtained from all patients in order to be eligible for the study and prior to any study procedures.

^c A limited physical examination may be conducted. Any abnormality identified should be recorded on the eCRF. New or worsened clinically significant abnormalities should be recorded as adverse events, if appropriate.

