## **2.4 ANALYSIS TIMING**

The final analysis will be conducted after all patients completed the study visits including safety follow-up visit and the optional substudy visits. Database lock will occur several weeks after the last patient last visit to clarify all outstanding queries. In addition to the final analysis, two interim analyses were performed: 1) when 20% of patients completed their 48-week visit, and 2) when all patients completed their 48-week visit.

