#### **4.1.2        Modified Intent-to-Treat Population**

The modified ITT (mITT) population is a subset of the ITT population which excludes patients who discontinued ocrelizumab treatment early without any protocol-defined events for reasons other than death and lack of efficacy.

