##### **4.4.1 Primary Efficacy Endpoint**

The proportion of patients who are free from a protocol-defined event during a 96-week period will be calculated and presented along with a two-sided 95% Clopper-Pearson exact confidence interval. Data from unscheduled visits within each respective 24-week interval will be included in the evaluation of the endpoint. Analyses will be performed for the mITT population. Patients are considered to have a protocol-defined event during the 96-week period if they discontinue due to lack of efficacy or death despite without a protocol-defined event as defined below.

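### The 4% half-width with 80% probability in SAP 2.3 does not hold, at the planning value of 45%, for the Clopper-Pearson interval on the mITT population that SAP 4.4.1 specifies

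*SAP*

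**What the plan says.** SAP 2.3 assumes that 45% of patients are event-free over 96 weeks and states that "the probability that half-width of 95% confidence interval is at most 4% is 80%, the required sample size for this study is n=600". It refers to the protocol for details and does not name an interval method.

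Protocol 6.1 makes the same statement and adds the unrounded figure: "if the proportion is 45%, the corresponding sample size is 598.86 (rounded to 600 for recommended number". If the true proportion is below 45%, it says, "the required sample size should be lower than 600 patients to achieve the same precision". It does not name the interval in its text either, and Protocol 6.5.4 mentions only a two-sided 95% CI. Figures 3 and 4, which display the calculation, are not shown in the copy reviewed.

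SAP 4.4.1 settles both open choices for the primary analysis. The proportion is to be "presented along with a two-sided 95% Clopper-Pearson exact confidence interval", and the population is the mITT. SAP 4.1.2 defines the mITT as a "subset of the ITT population which excludes patients who discontinued ocrelizumab treatment early without any protocol-defined events", except where the reason for stopping was death or lack of efficacy. Protocol 4.6.3 says: "Patients who discontinue study treatment prematurely will not be replaced". Neither sample-size section allows for these exclusions.

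For the shorter-infusion substudy, the table in Protocol Appendix 2 does name its method: "The 95% CIs for the IRR (%) are calculated based on the Clopper and Pearson method".

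**The concern.** The SAP fixed an interval method and an analysis population for the primary endpoint but carried over the protocol's precision statement unchanged. Clopper-Pearson intervals are wider than large-sample intervals at the same n, and the mITT can only be smaller than the treated population. Both changes widen the interval relative to the stated target.

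The study is single-arm with no hypothesis test on the primary endpoint, so precision is the only justification given for 600 patients. A reader of SAP 2.3 would take the 4% figure as a property of the planned primary analysis, and at the planning value it is not.

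**Working it through.** **Inputs.** Event-free proportion p = 0.45, 95% confidence, target half-width 0.04, probability 80%, n = 600 (SAP 2.3; unrounded 598.86 in Protocol 6.1). Interval and population: Clopper-Pearson on mITT (SAP 4.4.1, 4.1.2). Half-width means (upper limit − lower limit)/2. The size of the mITT is not given, so exclusions of 0%, 5% and 10% of 600 are used as assumptions.

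**Step 1: reproduce the plan's figure.** The Wald half-width is 1.96 × √(p̂(1 − p̂)/n). At 270/600 it is 1.96 × √(0.45 × 0.55/600) = 3.98%. The probability that it is at most 4% is the sum of Binomial(n, 0.45) probabilities over all outcomes x that meet the limit:

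| n | P(Wald half-width ≤ 4%) |
|---|---|
| 597 | 74.1% |
| 598 | 82.6% |
| 600 | 97.9% |

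The 80% mark is first reached at 598, which is consistent with 598.86. That the sponsor used a Wald-type interval is an inference, since the figure is not available.

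**Step 2: the planned interval with all 600 patients.** The Clopper-Pearson limits for x of n are the 2.5% quantile of Beta(x, n − x + 1) and the 97.5% quantile of Beta(x + 1, n − x).

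- At 270/600 the interval is 40.97% to 49.08%, a half-width of 4.06%.
- The half-width is at most 4% only if x ≤ 241, an observed 241/600 = 40.2% or lower.
- At p = 0.45, P(X ≤ 241) = 0.95%.
- For 80% probability at p = 0.45, 619 patients give 71.3% and 620 give 80.2%, so 620 are needed.
- Over all possible results at n = 600, the half-width never exceeds 4.08%.

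**Step 3: dependence on the true proportion (Clopper-Pearson).**

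| True p | P(half-width ≤ 4%) at n = 600 | Analysed patients needed for 80% |
|---|---|---|
| 0.45 | 0.95% | 620 |
| 0.42 | 19% | 614 |
| 0.40 | 55% | 607 |
| 0.35 | 99.6% | 581 |

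At p = 0.38 the probability is 87%. Solving P(X ≤ 241) = 0.80 gives p = 0.386. Below about 38.6% the stated 80% is met at n = 600. Between there and 45%, more than 600 patients are needed.

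**Step 4: mITT exclusions (assumed shares).** If a share e is excluded and all of those patients would otherwise have counted as event-free, the proportion becomes (0.45 − e)/(1 − e). This is 42.1% at e = 5% and 38.9% at e = 10%. The alternative keeps 45%.

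| Excluded | n analysed | Half-width, exclusions taken from the event-free | Half-width, 45% kept | Maximum over all results |
|---|---|---|---|---|
| 5% | 570 | 4.13% | 4.16% | 4.18% |
| 10% | 540 | 4.19% | 4.28% | 4.30% |

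**Step 5: the substudy table.** The listed limits for 1 to 7 of 100 reproduce exactly with Clopper-Pearson (1/100: 0.03 to 5.45; 7/100: 2.86 to 13.89). There, the stated precision does match the planned interval.

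**The case against.** The strongest reply is that the contrast between 1% and 80% comes from a sharp cut-off. The target is a whole number, the Clopper-Pearson half-width at n = 600 never exceeds 4.08%, and a threshold of 4.1% would always be met. Planning with a large-sample formula and reporting an exact interval is common practice. SAP 2.3 can be read as a record of how 600 was derived, and that derivation reproduces. The study is descriptive, no success rule uses 4%, and the actual interval will be published.

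Most of this stands, and it is why the point is minor. It does not rescue the sentence, which sets a limit of 4% and attaches an 80% probability to it. A half-width of 4.06% fails that limit.

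Three further objections stand in part:

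- The variance argument in Protocol 6.1 is right in direction: the required number falls as p falls below 45%, with either interval. Only the claim that it then lies below 600 fails, and only for Clopper-Pearson between about 38.6% and 45%. The protocol itself never adopted that interval.
- The exclusion shares are assumptions. The mismatch, however, is already present with no exclusions.
- Figure 3 may name the interval method. If it does, identifying the method behind 598.86 only requires repeating it in the text.

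**Conclusion.** The precision statement in SAP 2.3 is wrong as written for the analysis in SAP 4.4.1. At 45% event-free and 600 analysed patients the half-width is 4.06%, with about a 1% probability of being at most 4%. The shortfall against 4% is about 0.06 percentage points with no exclusions and up to 0.3 points if 10% are excluded.

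The main result rests only on figures in the documents. It is specific to the upper part of the plausible range: at a true proportion of about 38.6% or lower the stated 80% is met with 600 analysed. The figures for a reduced mITT rest on assumed exclusion shares, and the attribution of 598.86 to a Wald-type interval is inferred. Severity is minor: a stated figure needs correcting, but there is no serious loss of precision.

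**What to change.** In SAP 2.3, and in Protocol 6.1 if it is amended again, name the interval behind 598.86 and then add wording such as:

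> The planned analysis uses the Clopper-Pearson interval on the mITT population. With 600 analysed patients its half-width is about 4.1% at 45% event-free; if 5% or 10% of patients are excluded from the mITT, it is at most about 4.2% or 4.3%.

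No change to enrolment, interval method or analysis population is needed. The cost is two sentences, and a stated half-width about 0.1 to 0.3 percentage points less favourable. Only the wording can change now: SAP 2.4 reports that the second interim analysis was performed "when all patients completed their 48-week visit", so enrolment had already ended.

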## **2.4 ANALYSIS TIMING**

The final analysis will be conducted after all patients completed the study visits including safety follow-up visit and the optional substudy visits. Database lock will occur several weeks after the last patient last visit to clarify all outstanding queries. In addition to the final analysis, two interim analyses were performed: 1) when 20% of patients completed their 48-week visit, and 2) when all patients completed their 48-week visit.

## **3. STUDY CONDUCT**

### **3.1 RANDOMIZATION**

No randomization is planned. All patients will receive ocrelizumab.

### **3.2 INDEPENDENT REVIEW FACILITY**

Not applicable.

### **3.3 DATA MONITORING**

Not applicable.

## **4. STATISTICAL METHODS**

For continuous variables, descriptive statistics (e.g., mean, median, standard deviation [SD], n, 25th and 75th percentiles, minimum, maximum) will be calculated and summarized. For categorical variables, the number and percentage in each category will be displayed. Statistical methods for analysis of efficacy variables are detailed in the Efficacy Analyses section below.

Planned analyses for the shorter infusion sub-study will be described in Appendix 6.

## **4.1 ANALYSIS POPULATIONS**

The efficacy analyses will be performed using the intent-to-treat (ITT) or modified ITT (mITT) population. The per-protocol (PP) population will be used for sensitivity efficacy analyses for the primary endpoint only) in order to evaluate the influence of major protocol violators on efficacy of ocrelizumab. The safety analyses will be performed using the safety population.

### **4.1.1 Intent-to-Treat Population**

All enrolled patients who received any ocrelizumab will be included in the ITT population. Patients who prematurely withdrew from the study for any reason and who did not have any assessments for any reason will still be included in the ITT population as long as patient received ocrelizumab.

#### **4.1.2        Modified Intent-to-Treat Population**

The modified ITT (mITT) population is a subset of the ITT population which excludes patients who discontinued ocrelizumab treatment early without any protocol-defined events for reasons other than death and lack of efficacy.

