6.7 HANDLING OF MISSING DATA

The following guideline will be used when dealing with missing data related to the protocol-defined event in the primary efficacy endpoint. Patients who complete the treatment period will be considered as having a protocol-defined event if any of the following are reported during the 96-week *study*: at least one protocol-defined relapse, Gd-enhancing T1 lesions, new and/or enlarging T2 lesions, or CDP. Otherwise, the patient will be considered as being protocol-defined event free.

Patients who discontinue treatment early and have at least one event before early discontinuation will be considered as having a protocol-defined event. *Details of missing data handling for patients who discontinue treatment early and do not have any event before early discontinuation* will be specified in Statistical Analysis Plan.

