## **2. STUDY DESIGN**

This study is a prospective, multicenter, open-label, effectiveness and safety study in patients with RRMS who have had a suboptimal response to an adequate course of a DMT. This study will be conducted in North America.

An adequate course of prior DMT is defined as the same DMT administered for at least 6 months. Ocrelizumab will be administered as an initial dose of two 300-mg infusions (600 mg total) separated by 14 days (i.e., Days 1 and 15) followed by one 600-mg infusion every 24 weeks for the study duration.

Patients will be assessed for effectiveness and safety every 24 weeks as described in the schedule of assessment in [Appendix 2](#).

The study will consist of the following periods, described in detail below:

1. Screening period: up to 4 weeks.
2. Treatment period: open-label treatment period of 96 weeks (4 doses).
3. Safety follow-up period (additional B cell monitoring not applicable to protocol v5 patients): observation after the last infusion of study drug for patients who discontinue or who chose not to continue with commercially available ocrelizumab (if approved) at the end of study.
4. Eligible patients can be enrolled into an optional shorter infusion substudy to explore the effect of a shorter infusion of ocrelizumab on the rate and severity of IRRs.

Detailed study design, outcome measures and statistical analysis plan of the shorter infusion substudy will be described in Appendix 6.

[figure not shown]

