#### **4.4.2 Secondary Efficacy Endpoints**

The mITT population will be used for secondary efficacy endpoints of the proportion of patients free from a protocol-defined event during the first 24-week and 48-week period.

Analyses of all other secondary efficacy endpoints will be performed using the ITT population.

The proportion of patients free from a protocol-defined event during the first 24-week and 48-week will be presented along with a two-sided 95% Clopper-Pearson exact confidence interval. Same analysis method of the primary efficacy endpoint will be applied to the 24-week and 48-week outcomes. Note that event during the first 24-weeks will not include CDP events due to no confirmatory EDSS score can be observed within the first 24-weeks. A histogram of the percent of patients who are event free at weeks 24, 48, and 96 will be produced.

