#### **4.4.5 Subgroup Analyses**

The primary and all secondary outcomes will be analyzed for the following subgroup for the mITT population:

Last DMT before enrollment: Fingolimod vs. Other

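### One modified ITT set, defined by what happens up to Week 96, is reused for the Week 24 and 48 event-free proportions and for every secondary outcome in the subgroup analysis

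*SAP*

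**What the plan says.** The SAP has one mITT set. It is the ITT set but "excludes patients who discontinued ocrelizumab treatment early without any protocol-defined events for reasons other than death and lack of efficacy" (Section 4.1.2). Membership therefore depends on whether the patient stopped early, why, and whether an event was ever recorded. Section 4.2 counts mITT once, not by visit.

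- **Weeks 24 and 48.** Section 4.4.2: "The mITT population will be used for secondary efficacy endpoints of the proportion of patients free from a protocol-defined event" at those visits, and "Same analysis method of the primary efficacy endpoint will be applied to the 24-week and 48-week outcomes".
- **Other secondary endpoints, overall.** Section 4.4.2: "Analyses of all other secondary efficacy endpoints will be performed using the ITT population".
- **Subgroup (last DMT fingolimod versus other).** Section 4.4.5: "The primary and all secondary outcomes will be analyzed for the following subgroup for the mITT population".
- **Patients kept as failures.** Protocol 6.7: "Patients who discontinue treatment early and have at least one event before early discontinuation will be considered as having a protocol-defined event". SAP 4.4.1 adds: "Patients are considered to have a protocol-defined event during the 96-week period if they discontinue due to lack of efficacy or death". Protocol 6.7 leaves the remaining early leavers, those without an event, to the SAP, in a paragraph about the primary endpoint.
- **What counts as early.** SAP Section 2 has "Treatment period: open-label treatment period of 96 weeks (4 doses", while the synopsis reproduced in SAP 2.1 and Protocol 3.1 give 72 weeks for the same four doses. Section 4.1.2 does not say which applies.

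**The concern.** Inclusion in a Week 24 analysis should not depend on what happens after Week 24. Under the single set it does, and the dependence is lopsided: of two patients who were both event-free at Week 24 and both left at Week 60, the one who had an event in between is kept and the one who did not is removed. Missing data cannot be the reason, because both patients' Week 24 status is known.

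The subgroup rule raises a separate problem. Five time-to-event endpoints, the annualized relapse rate, the T1 and T2 lesion counts and T2 volume are analysed in ITT overall but in mITT by last DMT, with no reason given. The Kaplan-Meier method keeps event-free early leavers and censors them; in the subgroup they have been taken out beforehand.

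This is a single-arm estimation study. There is no comparator in which the same error would cancel.

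**Working it through.** **Yardstick.** Protocol 6.1 plans a 95% CI half-width of 4 points at 45% with 600 patients. 1.96 × √(0.45 × 0.55 / 600) = 0.0398, and requiring that width with 80% probability gives n = 598 (exact binomial) against the stated 598.86, rounded to 600. The planned precision reproduces.

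**Step 1: membership.**

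| Patient | Known status at Weeks 24 and 48 | In mITT | Counted at Weeks 24 and 48 |
|---|---|---|---|
| A: no event, stops at Week 60 (not death or lack of efficacy) | event-free | no | deleted |
| B: event at Week 55, stops at Week 60 | event-free | yes | event-free |

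**Step 2: direction.** Let n patients be followed to the visit or have an event before it, with a of them event-free there. The rule removes m patients like A from both counts, and (a − m)/(n − m) < a/n whenever a < n. Example: 600 patients, 480 event-free (80%), 30 deleted: 450/570 = 78.9%.

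**Step 3: size, constant hazards.** From the documents: 600 patients, 45% event-free at Week 96. Assumed: dropout d = 10% by Week 96, independent of outcome, *early* meaning before Week 96.

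- −ln 0.45 = 0.7985; −ln 0.90 = 0.1054; sum 0.9039; e^(−0.9039) = 0.405.
- All excluded: (0.1054/0.9039) × (1 − 0.405) = 0.0694, about 42 of 600.
- Week 24: on treatment and event-free 0.405^(1/4) = 0.7978. Later deleted: 0.1166 × (0.7978 − 0.405) = 0.0458, about 28 patients. Reported: (0.7978 − 0.0458)/(1 − 0.0694) = 80.8%. True: 0.45^(1/4) = 81.9%. Bias −1.1 points.
- Week 48: 0.405^(1/2) = 0.6364. Later deleted: 0.1166 × (0.6364 − 0.405) = 0.0270, about 16 patients. Reported: (0.6364 − 0.0270)/0.9306 = 65.5%. True: 67.1%. Bias −1.6 points.
- At 5% dropout the biases are −0.5 and −0.8; at 20%, −2.4 and −3.4.

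**Step 4: other event timings.** Two assumed profiles at Weeks 24/48/72/96 are 0.62/0.55/0.52/0.45 and 0.80/0.65/0.57/0.45, with uniform dropout and with or without an MRI at withdrawal. Reported value at week w = [(1 − d·w/96)·S_w − share deleted after w] / (1 − share excluded).

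Largest case at 10% (first profile, every leaver scanned, straight lines between visits):

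- Excluded: 0.1 × (0.81 + 0.585 + 0.535 + 0.485)/4 = 0.0604.
- Week 24: deleted later 0.1 × (0.585 + 0.535 + 0.485)/4 = 0.0401; (0.975 × 0.62 − 0.0401)/0.9396 = 60.1% against 62%, −1.9 points.
- Week 48: deleted later 0.1 × (0.535 + 0.485)/4 = 0.0255; (0.95 × 0.55 − 0.0255)/0.9396 = 52.9% against 55%, −2.1 points.

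Across the cases at 10%, 24 to 30 patients with known event-free status are deleted at Week 24 and 15 to 18 at Week 48. If *early* means before Week 72, the bias for 5% to 10% dropout is 0.4 to 1.4 points at Week 24 and 0.5 to 1.5 at Week 48.

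**Step 5: subgroup basis, 10% dropout.**

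- Composite Kaplan-Meier at Week 96 (simulation, constant hazards): 45.0% in ITT, 43.5% in mITT. With almost no early censoring left, the curve returns the mITT proportion, 0.9 × 0.45/0.9306 = 43.5%. The other profiles give −1.2 to −1.6 points.
- Lesions per scan, if deleted scans carry no lesions: inflation is 1/(1 − deleted share of scans). Second profile, no withdrawal scan: deleted scans per patient 0.1 × (0.80/4 + 2 × (0.65 + 0.57)/4) = 0.081; all scans 0.975 + 0.95 + 0.90 = 2.825; 1/(1 − 0.081/2.825) = 1.030. Range 2.4% to 3.0%.
- Relapse rate: inflation is (1 − w·k)/(1 − w), where w is the deleted share of exposure and k the deleted patients' relapse rate over the overall rate. With k = 0 the simulation moves an assumed 0.150 to 0.155, about 3%; with k = 1 there is none.

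**The case against.** - **"Same analysis method of the primary efficacy endpoint will be applied to the 24-week and 48-week outcomes" may mean that the exclusion is re-applied at each visit.** That is possible, and further handling rules sit in DAP Module 2, which is not among the documents. But the sentence names a method, the same section names the population, and no visit-specific set is stated. The point therefore holds for the SAP as written; it does not establish what the programs will do.
- **The ITT Kaplan-Meier curve already covers Weeks 24 and 48.** This stands in part. Time to protocol-defined event is an ITT endpoint, plots are planned, and the Appendix 4 code saves the survival estimates. A reader can gauge the effect. The match is not exact: that curve does not count death or lack-of-efficacy discontinuation as events, and it dates disability progression at onset whereas the Week 24 proportion leaves progression out. Nor does it correct the reported proportions.
- **The bias is conservative and its size is assumed.** Also fair. The only related figure in the protocol is 3.5% discontinuation for adverse events in the pooled Phase III studies. The formulas delete every event-free leaver, although those leaving for death or lack of efficacy stay in, so they slightly overcount.

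Three stronger readings are tempting, and the documents do not support them.

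- A reader might infer that subgroup results cannot be compared with overall results. The effects in Step 5 are too small for that, and both subgroup levels share one basis.
- A reader might infer that every deleted scan is lesion-free by definition. SAP 4.4.1 limits events to those on treatment, while Protocol Appendix 1 requires an MRI at discontinuation unless one was done within 8 weeks. Whether a lesion on that scan counts is not stated, so the lesion figure is an upper guide.
- A reader might infer that the Week 96 primary analysis breaks the protocol. Protocol 6.7 leaves event-free early leavers to the SAP, so that choice was open.

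**Conclusion.** The point holds for the SAP as written. At Weeks 24 and 48 the single mITT set deletes patients whose status at the visit is known, with no missing-data reason. Relative to a visit-specific analysis the shift is downward whatever the dropout mechanism (Step 2). Relative to the true proportion it is downward if dropout is independent of outcome: about 0.5 to 2.0 points at Week 24 and 0.7 to 2.1 at Week 48 for an assumed 5% to 10% dropout before Week 96, against a planned half-width of 4 points for the primary endpoint. If dropout is related to outcome, the net direction is not known.

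In the subgroup analysis, nine secondary endpoints sit on a different basis from their overall analysis. At 10% dropout the effect is about 1 to 2 Kaplan-Meier points, up to about 3% on the lesion rate, and between nil and about 3% on the relapse rate. The primary endpoint and the Week 24 and 48 proportions are mITT both overall and by subgroup, so the mismatch does not touch them.

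Severity is minor to should-fix: the rule is faulty and cheap to repair, but at modest dropout the numbers move little.

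**What to change.** 1. **Section 4.4.2, Weeks 24 and 48.** Include every ITT patient who was followed to the visit or had an event before it, whatever happens later. Count discontinuation for death or lack of efficacy before the visit as an event, in line with Section 4.4.1. In the constant-hazard case this gives 0.7978/(1 − (0.0694 − 0.0458)) = 81.7% at Week 24 and 0.6364/(1 − (0.0694 − 0.0270)) = 66.5% at Week 48, leaving biases of 0.2 and 0.6 points. Across the other profiles at 10% dropout the remaining bias is 0 to 0.3 and 0.3 to 0.9 points.
2. **Section 4.4.5.** Use for each secondary endpoint the population of its overall analysis: ITT for the time-to-event, relapse-rate and MRI endpoints.
3. **Optional at Week 96.** Keep the mITT proportion as primary. Show beside it the ITT Kaplan-Meier estimate and two bounds, with the excluded patients counted all as events and all as event-free. Reconcile the 72-week and 96-week statements of the treatment period so that *early* in Section 4.1.2 has a defined time point.

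The cost is SAP text before database lock and a few extra outputs, with no new data and no change to the primary estimator. SAP 2.4 records two interim analyses already performed, the second once all patients had completed Week 48, so the amendment should state that the changes were made after them.
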